Student projects involving human participants that are conducted solely to fulfill course requirements and to receive a course grade and will not be shared outside the classroom and/or the Syracuse University community do not require IRB review. For additional information please consult: [Student-Projects](#)

None of the above. Other purpose (explain): _____

NOTE REGARDING APPLICATION PREPARATION: When there is more than one researcher listed in the protocol as part of the research team, please avoid the use of pronouns or references to "the research team/member/s of the research team" or the use of similar terminology. Instead, all such references should include the names of the members of the research team listed in either Sections 1 or 6 of the protocol application as appropriate.

3. Study Rationale

3.1. Using non-technical language, describe the objective of this proposed research including purpose, research question, hypothesis, etc. From your description, the IRB should be able to determine how this proposed study adds to the knowledge on the research topic in order to judge the risks and benefits to the research participants. **NOTE:** A reference list citing relevant background information must be provided as an appendix with this application.

As of 2015 an estimated 2 billion individuals were overweight (body mass index [BMI] $\geq 25 \text{ kg/m}^2$) and one third of them obese (BMI $\geq 30 \text{ kg/m}^2$).¹ Obesity has become a serious health concern due to its related comorbidities including cardiovascular disease (CVD), and type 2 diabetes (T2D).²⁻⁵ While adolescents and young adults are considered low risk for development of CVD, individuals with obesity are still at greater risk of CVD development

than individuals without obesity.⁶ Changes to dietary and fitness habits are currently the first line recommendations to prevent weight gain and improve cardiometabolic health in adolescents and young adults.⁷

Caloric restriction (CR) (reducing caloric intake up to 50% of normal calorie intake per day)⁸ is a common dietary interventional approach for weight management and cardiometabolic health improvement in adolescents and adults with obesity.⁹ However, studies have shown that CR is hard to maintain, and individuals tend to re-gain the weight after the intervention is completed.¹⁰ Time restricted eating (TRE) has been suggested as an alternative to CR.¹¹ TRE, a type of short-term fasting, is defined as periods of no energy (calories) intake followed by periods of ad libitum (as much as desired) energy intake.¹² The fact that TRE does not intentionally limit energy intake, while CR does, could make it more appealing to individuals with respect to adherence, acceptability and efficacy.¹³ TRE has been shown to be an effective strategy in reducing body fat percentage and waist circumference in adolescents and adults with obesity.^{13,14}

Moreover, high-intensity interval training (HIIT), repetitions of a short period of intense activity followed by a low intensity break, has shown to be effective in improving cardiometabolic health (including lipids, blood pressure, and insulin sensitivity) in adults with obesity compared with other traditional exercise.¹⁵ In addition to its benefits on cardiometabolic health, previous studies have suggested that HIIT can be a time-efficient strategy to enhance body composition and cardiopulmonary fitness in adults with obesity.¹⁶

However, it is unknown if TRE or HIIT will produce a greater improvement of cardiometabolic health. Therefore, the goal of this proposed study is to examine the independent and combined effects of a 4-week TRE and HIIT intervention on cardiometabolic biomarkers in adolescents and young adults.

4. Methods

4.1. Provide a detailed description of what participants will be required to do; including any technical terms or procedures.

Participants: A total of 50 adolescents (age 14-17 years old with sex- and race-specific BMI percentile $\geq 85^{\text{th}}$) and young adults with overweight and obesity (age 18 to 30 years old with BMI $\geq 25 \text{ kg/m}^2$) will be recruited for the study. This is a randomized control trial with 50 participants randomly being assigned into 3 groups: TRE intervention (n=20) or HIIT intervention (n=20), and control (n=10). The following below outlines what participants will be asked to do during each lab visit and during the 4-week of intervention.

A) Pre-lab Contacts:

Participants will be recruited via flyers and social media posting. Those who are interested in participating in the study will tell the researchers if they are interested in participating in the research study or will reach out via email. We will explain the purpose of the study, as well as study procedures to the potential participant. We will also provide copies of the written consent document and confirm that participants meet the inclusion criteria during this initial exchange. During this initial exchange, we will verify that the potential participant has met each of the inclusion criterion, listed on the flyer. If the participants need further clarity, or have more questions, we will provide them with a phone number for them to call us so we can answer their questions with more detail. If the potential participant expresses continued interest in enrolling in the study, we will schedule a time for them to come to the Clinical Research Laboratory (CRL) on the Syracuse University campus (Women's Building Room 303) so that we may guide them through the written consent document and begin the consent process.

If participants are interested and eligible, they will be instructed via email (1-2 days prior to actual visit days) to wear comfortable, normal, everyday athletic wear for their in-person visits. Participants will be asked to come to the SUNY Upstate Clinical Research Unit followed by SU Clinical Research Laboratory Visit after an overnight fast of 10-12 hours.

B) Pre-Intervention Lab Visits:

All data are collected following standardized procedures and by the same investigators at all timepoints to minimize potential errors of measurements. All participants will provide written informed consent prior to study involvement in accordance with university institutional review board guidelines. The following outlines the specific measurements that will be taken and the specific protocol for lab visit one.

(a) SUNY Upstate Visit (Clinical Research Unit):

After 10- to 12-hr of overnight fasting, participants will come to SUNY Upstate (Clinical Research Unit; Institute For Human Performance Rm# 1223) to undergo their 2-hour oral glucose tolerance test (OGTT) with multiple blood draws (venous blood samples will be obtained at -15, 0, 30, 60, 90 and 120 min), directed by [name] (a director of Clinical Research Unit) and/or registered nurses ([name], CCRC). At time 0 min, participants will drink a standard 75 g glucose solution purchased commercially. Youth will be administered 1.75 g glucose per kg (not to exceed 75 g). After the last blood sample ($t = 120$ min), participants will be provided a snack and allowed for the Syracuse University Visit.

Note that [name], a director of Clinical Research Unit, upon [name] agreement, will submit a separate IRB application to the SUNY Upstate Medical School.

(b) Syracuse University Visit (Clinical Research Lab & Human Performance Lab):

- After the SUNY Upstate Visit (at the Clinical Research Lab at SU), participants' standing height and weight will be assessed without shoes, wearing light clothing, to the nearest 0.1 cm using a stadiometer and balance beam scale to the nearest 0.1 kg, respectively. Body composition and visceral fat will be estimated by multi-frequency bioelectrical impedance (BIA) InBody (Inbody 770, South Korea). For the InBody assessment, participants stand barefoot on the platform of the device with the soles of their feet on the electrodes. They then grasp the handles of the unit with their thumb and fingers to maintain direct contact with the electrodes and remain still for ~1 min while keeping their elbows fully extended and their shoulder joint abducted to around 30° angle (Figure 1).

- We will measure waist and hip circumferences. Participants will stand straight with their arms out while a tape measure is wrapped around their waist and hip. Measurements will be taken to the nearest cm.

- Participants' lipid profile will be collected by Cholestech Analyzer using a blood sample obtained via a finger stick (Figure 2). Participants will select which finger they wish to use, then the researcher (wearing gloves) will clean the fingertip with an alcohol swap. Then, the researcher will "stick" the finger to draw blood. The first drop of blood will be wiped away, and the second drop will be collected and used for analysis. This may cause slight discomfort but is relatively quick and painless. After this the researcher will provide a clean gauze, to clean the area, and a band-aid (if needed).

- We will gain parameters related to cardiovascular function by using a blood pressure monitor. Participants will be asked to sit quietly for five minutes with minimal movement. After this we will place the cuff on their right upper arm (bicep area) and start the measurement. The cuff will inflate, deflate, and then reinflate again. We will ask participants not to move during this process. All of the equipment will be disinfected prior to distribution with disposable wipes (antiviral/antibacterial/antifungal) by a researcher wearing gloves before and after every time collection is performed on a participant.

- We escort participants across the hall (less than 10 feet) to the Human Performance Lab where we will take the following pre-clinical marker (Carotid-femoral pulse wave velocity [PWV]) of CVD. Participants will be escorted to a padded exam table. They will lie down and rest for approximately 5 minutes. Blood pressure in the upper arm will be measured using an automated device with a cuff that wraps around the upper arm and inflates and deflates, applying pressure to the arm. Next, we will obtain blood pressure in the wrist (radial artery), neck (carotid artery), and upper leg (femoral artery) using an applanation tonometer (SphygmoCor, AtCor Medical). This technique is non-invasive, requiring approximately 5 minutes for completion. A picture of the technique is attached. A tonometer is a very sensitive force transducer (similar in appearance to a watch battery affixed to a pen). This pen is placed over the artery of interest providing an accurate recording of the blood pressure wave. With each pulsation of the arterial pulse, a force is generated against the tonometer. The tonometer records this force wave

and reconstructs it into a pressure wave. From this wave, we can estimate blood pressure in this artery and calculate the stiffness (or how elastic the artery is). This measure takes 5-minutes to complete.

C) Randomization:

Upon completion of the Pre-Intervention Lab Visit, participants will be randomly assigned into one of three groups: (a) TRE, (b) HIIT, and (c) Control. The randomization will be done separately for adolescents and young adults [with the exploratory purpose of future analysis on age-specific difference in interventional effects on cardiometabolic health]. Within each group, we anticipate that there will be an equal number of adolescents and young adults.

(a) Time Restricted Eating (TRE) trial:

Participants randomized into the TRE group will be instructed to consume all their calories within a 10-hour period. We will instruct participants that they can choose their time-window (early TRE [7am – 5pm] or late TRE [1pm – 11pm]), but it must remain constant for the duration of the study. Further, we will give no restrictions on the type of foods and/or the quantities individuals can consume. We will ask individuals to maintain their diet for the duration of the study. Participants will be given clear instructions on their diet and how to use the “MyFitnessPal” application. Participants will have their total daily energy requirement calculated using the following formula (Basal metabolic rate [BMR] x activity level) and will be told to eat that amount within their allotted time window. BMR will be calculated when participants have their body composition taken by the InBody. Participants will be told to start their 4-week diet the following day after visit.

(b) High Intensity Interval Training (HIIT) trial: The 4-week HIIT intervention will use a stationary bicycle performed 3 times/week (a total of 12 sessions over the 4-week), performing at the CRL. All participants will perform a 20-minute HIIT protocol (20 repetitions of 10-seconds work time followed by 50-seconds resting/active recovery for the first two weeks, and 10 repetitions of 20-seconds work time followed by 100-seconds resting/active recovery for the rest of two weeks; targeted 90% HR_{max}) after 5-minute warm-up (10% HR_{max}). The supervisor (PI: [name] and/or Graduate researcher: [name]) will provide encouragement and supervision for exercise adherence. Heart rate (Polar, Polar Electro Oy, Kempele, Finland) and rating of perceived exertion (RPE; detail described in the questionnaire section) will be recorded.

(c) Control group: Participants randomized into the control group will be told to maintain their daily lifestyle and dietary habits for the duration of the four weeks.

D) Post-Intervention Lab Visits:

Following completion of the 4-week intervention, individuals will be asked to come back to undergo same screening/measurements of the Pre-Intervention Lab Visit (SUNY Upstate and Syracuse University visits). An email will be sent to participants on their last day of the intervention with available time and dates for their visit. This will ensure all individuals will be tested with a similar fasting schedule, regardless of what group they were in.

4.2. Describe how you will have sufficient time to conduct and complete the research?

The anticipated time for each visit (Pre- and Post- Intervention Visits) will take approximately 5-6 hours including our measurements performed and transportation between SU and SUNY Upstate. PI ([name] [name]) and graduate researchers ([name], [name], [name]) haven already been involved in similar projects so that team members can split hours or days to secure successful completion of the study (performing study procedure and supervising participants during the intervention) in time. This study is designed to be completed in one year. We do not anticipate any issues around time constraints for completing this study. [name] has generally 2+2 teaching load with minimal service dedication thereby securing his time commitment to the research. [name] is a director of Clinical Research Unit at SUNY update and agreed (as a scientific consultant) that we will have all participants being underwent OGTTs at the cite (i.e., research/service cost: ~\$150, covered by [name] startup funds) will be paid to the Research Unit).

4.3. Surveys, interviews, questionnaires will be conducted:

No (Skip to 4.4)
 Yes Include all research instruments including surveys, questionnaires, sample interview questions, etc. as separate appendices. If the survey instrument is commonly used in your discipline, only provide a citation to the instrument.

4.4. Community Based Participatory Research (CBPR) is described as research that is conducted as an equal partnership between traditionally trained "experts" and members of a community. Is this research categorized as CBPR?

No. (Skip to 4.5)
 Yes. Please explain: _____
4.4.1. In CBPR research studies, the community participates fully in all aspects of the research process including conception, design, and analysis.
With this in mind, describe how you plan to engage community members in your research study:

4.4.2. Describe how you plan to provide community members with appropriate training for human subjects research? Include in your description what training will be provided.

4.4.3. Describe your plan to disseminate research findings with members of the community throughout the course of your study.

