The study design was developed over a series of in-person meetings; roles and responsibilities for all research personnel have been explicitly identified, as well as a timeline of activities. [name] has been informed of the protocol and specific research-related duties and functions and will be supervised by [name] [name] throughout all phases of the study. Prior to enrolling participants, we will hold regular lab meetings (weekly emails, Zoom meetings) to review specific roles.

6.5. Explain why you do not need additional qualified staff, other than those listed in Sections 1 and 6, to conduct your study.

[name], [name], [name], and [name] will be fully responsible for the primary study. Given its simplicity of data collection procedure, consent form, anthropometric and blood draw, will be collected by these four investigators.

7. Characteristics of Participants

7.1. Approximate Number of Participants to be recruited: 50

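### The protocol names no primary endpoint or main contrast, and its motivating question, its stated goal and its three randomised arms do not match

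*Protocol*

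**What the plan says.** Section 3.1 ends with two sentences of purpose. The first gives the gap in knowledge: "However, it is unknown if TRE or HIIT will produce a greater improvement of cardiometabolic health". The second draws the aim from it: "the goal of this proposed study is to examine the independent and combined effects of a 4-week TRE and HIIT intervention on cardiometabolic biomarkers". The form asks at this point for a research question and hypothesis; no hypothesis is written.

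Section 4.1 (Participants) assigns 50 people to three groups, "TRE intervention (n=20) or HIIT intervention (n=20), and control (n=10"). Section 4.1 C lists the same three groups and describes the comparator: "Participants randomized into the control group will be told to maintain their daily lifestyle and dietary habits for the duration of the four weeks". Section 7.1 repeats the total ("Approximate Number of Participants to be recruited: 50") without a derivation. The recruitment script in section 8.1 describes four groups, one of which does both interventions.

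Section 4.1 B sets out the measurements. At the glucose tolerance test (OGTT), "venous blood samples will be obtained at -15, 0, 30, 60, 90 and 120 min"; neither the analytes nor a summary index is named. Weight, body composition, visceral fat, waist, hip, a lipid profile and blood pressure follow, and then "we will take the following pre-clinical marker (Carotid-femoral pulse wave velocity [PWV]) of CVD". None of these is ranked. The only analysis given a status is the comparison between age groups, which section 4.1 C calls exploratory.

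**The concern.** The gap sentence and the goal sentence point to different contrasts. Which of TRE and HIIT improves health more is answered by comparing those two arms. The independent effect of each, in a trial with a no-intervention arm, is most naturally that arm against control. The answers can diverge: both arms may beat control without differing from each other, or they may differ while only one beats control. The third element of the goal, the combined effect, cannot be estimated from the three randomised groups.

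The outcome is a class of biomarkers, not a variable. With contrast and endpoint both open, a reader of the results could not tell which comparison was meant to answer the trial's question. A null finding on one could give way to a significant finding on another.

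**Working it through.** **Plan's own figure.** There is none to reproduce. The protocol states no alpha, power, effect size or SD, and gives 50 (20/20/10) without inputs.

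**Contrasts the arms can supply.**
- TRE against HIIT, 20 v 20: the gap sentence in 3.1.
- TRE against control, 20 v 10: the likely meaning of *independent* in the goal.
- HIIT against control, 20 v 10: the same.
- TRE plus HIIT against anything: named in the goal and described in the 8.1 script, but no such arm in 4.1.

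**Number of comparisons.** Counting one variable per named measure: OGTT, weight, body composition, visceral fat, waist, hip, lipids, blood pressure and pulse wave velocity make 9. Then 9 × 3 = 27. Splitting the OGTT, lipids or blood pressure into components would raise this.

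**Chance of at least one false positive.** Assumptions, none of them from the protocol: every comparison tested at two-sided 0.05 without correction, normal outcomes with equal pairwise correlation, and no true effect anywhere. Simulated with groups of 20/20/10 and pooled-variance t tests on 47 degrees of freedom, 6,000 replicates:

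| Endpoints | Tests | Correlation 0 | 0.5 | 0.8 |
|---|---|---|---|---|
| 1 | 3 | about 0.12 | – | – |
| 6 (one per domain) | 18 | 0.53 | 0.43 | 0.30 |

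The single-endpoint figure does not depend on the correlation. The six domains are OGTT, weight and body composition, circumferences, lipids, blood pressure and pulse wave velocity. For scale, three independent tests would give 1 − 0.95³ = 0.143; the simulated 0.12 is lower because the three contrasts share arms.

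**Precision of each contrast**, in SD units, with SE = √(1/n₁ + 1/n₂):
- TRE against HIIT: √(1/20 + 1/20) = 0.316.
- Either arm against control: √(1/20 + 1/10) = 0.387.
- Ratio: 0.387 / 0.316 = 1.22.

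**Difference detectable with 80% power**, two-sided 0.05:
- Normal approximation, (1.960 + 0.842) × SE: 0.89 SD for 20 v 20 and 1.09 SD for 20 v 10.
- Noncentral t: 0.91 SD and 1.12 SD.

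At a true difference of 0.8 SD, power by the t calculation is 0.69 for TRE against HIIT and 0.51 for an arm against control. Which contrast is main therefore changes what 50 participants can show.

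**The case against.** The strongest reply is that this is loose wording in an ethics application. Section 3.1 asks for non-technical language, and section 4.1 asks what participants will do, so its list is one of procedures and not of endpoints. A three-arm trial can compare each arm with control and the arms with each other, so gap and goal need not conflict. Contrast ordering, multiplicity methods and covariates usually belong in a statistical analysis plan, which may exist.

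Much of this stands. A reader might infer that the protocol sets up two rival deciding questions, but it calls neither one deciding, and comparison with no intervention is inferred from *independent* and the control arm. A reader might also infer that no claim would have a known false-positive rate. Under the assumed 0.05, each single test has a known rate; only the rate across the family is uncontrolled. The protocol contains no testing rule, so the family rates describe one way the data could be used, not a stated plan.

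Nor does 20/20/10 show that TRE against HIIT was meant to be main, since no reason for the split is given. The 22% gap in standard error compares contrasts within this design. Against an equal split (50/3 = 16.7 per arm, SE √(2/16.7) = 0.346), the control contrasts lose about 12% (0.387/0.346).

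The reply does not reach the core. The main comparison and primary endpoint are protocol content, and a later analysis plan cannot supply a combined arm that was never randomised.

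**Conclusion.** The concern holds in a limited form. Sections 3.1 and 4.1 do not fix what the trial is to conclude: no primary endpoint, no main contrast, and a goal containing one effect that the randomised arms cannot estimate. Sections 3.1, 4.1 and 8.1 must be reconciled on that last point.

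The count of about 27 comparisons follows from the listed measures and arms, taking one variable per measure. The standard errors follow from the allocation alone. The detectable differences also need the assumed alpha and 80% power. The family-wise rates, about 0.12 for one endpoint and about 0.3 to 0.5 for six, rest further on uncorrected testing, the chosen number of endpoints and the assumed correlation, and should be read only as illustration.

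The data would remain usable whatever is decided. What is at risk is the standing of any headline result, so the change should be made.

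**What to change.** Before outcome data are examined, amend sections 3.1 and 4.1 as follows.

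1. Name one primary endpoint from the measures already collected. A single OGTT-derived measure is one example; the protocol ranks no outcome, so the choice is the sponsor's.
2. Name the main contrast. Either TRE against HIIT decides, with the two control contrasts tested afterwards in fixed order, or the two control contrasts are co-primary with Holm or Dunnett. Make the gap and goal sentences agree with the choice.
3. Remove *combined* from the goal, or reconcile it with the randomised arms and the section 8.1 script.
4. Label all other biomarkers secondary, reported as estimates with confidence intervals.

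The cost is a short wording amendment, with no added participants, visits or assays. The downside is that secondary results carry weaker claims and the sponsor can no longer choose the headline comparison after seeing the data.

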We are interested in how time restricted eating and high intensity interval training will impact the metabolic health of individuals under the age of 31, with a body mass index of 25 or higher. We will have one group randomly assigned into a group that only eats during a ten-hour window per day, one group that performs a high intensity interval training 20-minute workout three times per week, one group that does both, and one group that does neither. This study will last for four weeks. Before the intervention starts, and after the intervention is completed, we will ask you to come to the Clinical Research Lab (third floor of the Women's Building, room 303), where we will assess your height, weight, body composition. Then we will escort you to SUNY Upstate for a two-hour oral glucose tolerance test, where you will have your blood drawn every 30-minutes. Each of these two lab visits will take about three hours to complete. After each lab visit is finished, you will be compensated via Amazon gift cards.

If this still sounds like something you would be interested in, or if you have any additional questions, you can email me back or call me on the [contact]. I have attached the consent form to this email as well, so this way you can look it over at your leisure.

Thank you for your time and potential interest in our study.”

8.2. Describe who will recruit participants.

[name] will recruit participants.

8.3. Identify all applicable recruitment methods that apply: NOTE:Copies of all advertising materials including flyers, posters, ads, letters, scripts or detailed descriptions; including graphics **MUST be provided with your application. (See [SOP 036 for Recruitment/Advertising](#)).**

Flyers

E-mail

SU Today News Service

- Internet Posting
- Letter
- Telephone
- Other (describe): _____

- Posters
- Newspaper
- Radio

- Television
- Departmental Research Boards
- Social Media

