8.4. Will participants be compensated?

- No. (Skip to Section 9)
- Yes. If yes, answer 8.4.1. and 8.4.2. below.

Note: All information regarding compensation must be included in consent/assent documents.

8.4.1. If Yes, specify the method of compensation (e.g. monetary, course credit, gift card, toy, etc.), the amount of compensation, and how the compensation will be awarded (per task, per session, etc.).

Compensation will be given out after each visit via Amazon gift cards.

50 dollars will be given out after completion of visit one (pre-intervention visit).

50 dollars will be given out after participants complete the first two weeks of the intervention (with the exception of control group).

50 dollars will be given out after participants complete the last two weeks of the intervention (with the exception of control group).

50 dollars will be given out after completion of visit two (post-intervention visit).

In total, 200 dollars will be given out for participants who complete the study protocol. Participants in the Control will obtain 100 dollars upon their completion of the visits.

8.4.2. Describe how compensation will be awarded if the participant withdraws after beginning the study. Compensation cannot be contingent upon full participation and must be pro-rated in a manner that recognizes the time and effort of the participant prior to withdrawal. Provide a copy of the pro-rating schedule.

For the intervention group, there will be four time points for participants receiving compensation. The first and last compensation will be for the time and effort of one-time visit (i.e., one-day measurement visit). If participants come to the lab but are not able to complete all tasks or measurements during the visit, they will receive \$10 for their time and effort for the visit. The second and third compensation will require 2 weeks of intervention. Each compensation will be provided based on their time and effort with the pro-rating schedule below.

[HIIT intervention: lab visit] 1st week of intervention: \$8/day; 2nd week of intervention: \$9/day; 3rd week of intervention: \$8/day; 4th week of intervention: \$9/day

[TRE intervention: home-based food track survey] 1st week of intervention: \$3/day; 2nd week of intervention: \$4/day; 3rd week of intervention: \$3/day; 4th week of intervention: \$4/day

For the control group, the compensation will be given based on their one time visit so pro-rating schedule will not be applicable.

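### The goal promises the combined effect of TRE and HIIT, but no arm receives both, and the recruitment script describes a fourth group that the randomisation does not contain

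*Protocol*

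**What the plan says.** **Goal (Section 3.1).** The study is to "examine the independent and combined effects of a 4-week TRE and HIIT intervention on cardiometabolic biomarkers" in adolescents and young adults. The sentence just before gives a narrower reason for the trial: "it is unknown if TRE or HIIT will produce a greater improvement of cardiometabolic health".

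**Arms (Section 4.1).** The Participants paragraph divides 50 people into TRE (n=20), HIIT (n=20) and control (n=10). Part C, Randomization, repeats that "participants will be randomly assigned into one of three groups: (a) TRE, (b) HIIT, and (c) Control". The procedures under (a), (b) and (c) describe one intervention each for the first two arms and usual lifestyle and diet for the third.

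**Payment (Sections 8.4.1 and 8.4.2).** The pro-rating covers HIIT and TRE as separate interventions, and control is paid by visit. There is no schedule for a participant doing both.

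**Recruitment script (Section 8.1).** The e-mail lists a TRE group and a HIIT group, and then "one group that does both, and one group that does neither". That makes four groups.

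**The concern.** The goal names a quantity, the effect of TRE and HIIT given together, for which the design produces no data. This is not a detail that can be left to a statistical analysis plan, because no analysis can recover the mean outcome of a group that was never formed.

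Two things are at stake. First, the form's own instruction for Section 3.1 says that the IRB judges the study's contribution, risks and benefits from this description, so the IRB is being asked to credit knowledge that the trial cannot produce. If the wording stays, a report on the combined effect could rest only on an unstated assumption that the two effects add. Second, candidates, who may be as young as 14, are told at first contact of an assignment that they cannot receive.

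**Working it through.** **Inputs.** Arm sizes 20, 20 and 10 (Section 4.1); total 50 (Sections 4.1 and 7.1). The protocol gives no significance level, power, effect size or SD, so it has no power calculation to reproduce.

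**1. The plan's own total.** 20 + 20 + 10 = 50. The three arms use the whole sample and leave 0 of 50 for a combination.

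**2. Can the combined effect be estimated?** Let T = 1 for TRE and H = 1 for HIIT, and write the mean outcome as

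μ = β0 + β1·T + β2·H + β3·T·H.

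| Arm | n | T | H | T·H | Mean |
|---|---|---|---|---|---|
| Control | 10 | 0 | 0 | 0 | β0 |
| TRE | 20 | 1 | 0 | 0 | β0 + β1 |
| HIIT | 20 | 0 | 1 | 0 | β0 + β2 |
| TRE+HIIT | 0 | 1 | 1 | 1 | β0 + β1 + β2 + β3 |

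The T·H column is zero for all 50 participants, so the design matrix has rank 3 for 4 parameters. A contrast is estimable only if adding it as a row does not raise the rank:

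- TRE vs control (β1): estimable.
- HIIT vs control (β2): estimable.
- TRE vs HIIT (β1 − β2): estimable.
- Interaction (β3): not estimable.
- Combined vs control (β1 + β2 + β3): not estimable.

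This result depends on no assumption about variance or power, and a larger sample does not change it.

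**3. What precision do the three arms give?** Standard errors are in units of a common outcome SD. The detectable difference uses the noncentral t distribution with 50 − 3 = 47 degrees of freedom. It assumes two-sided 5%, 80% power, complete data and no adjustment for multiple comparisons. These are my assumptions, not the protocol's.

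| Contrast | SE | Detectable difference |
|---|---|---|
| One active arm vs control | √(1/20 + 1/10) = 0.387 | 1.11 SD |
| TRE vs HIIT | √(1/20 + 1/20) = 0.316 | 0.90 SD |
| Combined effect, additivity assumed | √(1/20 + 1/20 + 4/10) = 0.707 | 2.02 SD |

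The last row is (TRE − control) + (HIIT − control). The control mean enters twice, so its variance of 1/10 is multiplied by 4. The protocol does not propose this analysis. The row only shows what the one available workaround would give: an untestable assumption (β3 = 0) and a standard error nearly twice that of a single comparison with control (0.707 / 0.387 = 1.83).

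**The case against.** The strongest reply is that this is a slip of wording. Every operative section agrees on three arms, and the question posed just before the goal, TRE against HIIT, can be answered with them. A report could simply leave out the combined claim. That is a fair account of how small the repair is, and it is why the fix leaves the design alone. It does not make the goal correct as written.

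A second reply is that *combined* might mean both active arms pooled against control. That contrast is estimable: 40 vs 10, SE √(1/40 + 1/10) = 0.354 SD. But no section describes such pooling, while the script describes a group that does both interventions. The script makes the pooled reading unlikely.

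Third, the script says that the consent form is attached to the same e-mail, and written consent is taken later (Sections 4.1 and 9.6). Candidates may therefore be correctly informed before they enrol. The consent and assent forms are not in the copy reviewed, so this cannot be settled. What stands is that the script itself is wrong for a three-arm trial.

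Finally, the protocol does not say outright which design was intended. The weight of the text favours three arms, but the sponsor should confirm it.

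**Conclusion.** The concern holds. The goal, the randomisation and the recruitment script cannot all be right. With 0 of 50 participants planned for TRE plus HIIT, the combined effect and the interaction cannot be estimated (rank 3 of 4). This takes *combined* to mean both interventions in the same person, as the script does. The SEs and detectable differences also rest on the assumptions stated with them, but the main conclusion does not.

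The conflict is confined to the combined effect in the goal and the fourth group in the script. The comparisons of TRE with control, HIIT with control and TRE with HIIT are unaffected. It should be corrected before recruitment uses the script, because it concerns both the stated aim and what candidates are told.

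**What to change.** The sponsor should confirm the three-arm design that the operative sections already describe, and bring the other text into line:

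1. **Section 3.1:** remove *and combined* from the goal, and state it as TRE vs control, HIIT vs control and TRE vs HIIT.
2. **Section 8.1:** remove the group that does both from the script, so that it lists three groups.
3. **Flyer, consent and assent forms:** check for the same wording and correct it where found.

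**Cost:** an IRB wording amendment and a narrower claim, since the trial no longer says that it examines the combination. Sample size, arms, visits and budget do not change.

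If the sponsor does want the combined effect, the design itself must change, which goes beyond this fix. For orientation, take a 2×2 layout at N = 50 with cells of 12 or 13, 46 degrees of freedom and the other assumptions as above:

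- One cell against another, including combined vs control: SE √(1/12 + 1/13) = 0.400, detectable at about 1.15 SD. TRE vs HIIT would thus worsen from 0.90 SD, and a single intervention vs control would move from 1.11 SD.
- Main effect at the margins, 25 vs 25, valid only without interaction: SE √(2/25) = 0.283, about 0.81 SD.
- Interaction: SE √(2/12 + 2/13) = 0.566, about 1.62 SD.
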